16.1.3. SERIOUS ADVERSE EVENTS

Serious adverse events (SAEs) are those events recorded as “Serious” on the Adverse Events page of the eCRF. A summary of serious TEAEs by SOC and PT will be prepared, similarly to [Section 16.1.1](#) and [Section 16.1.2](#).

16.1.4. ADVERSE EVENTS LEADING TO DEATH

TEAEs leading to Death are those events which are recorded as “Death” on the Adverse Events page of the eCRF. A summary of TEAEs leading to death by SOC and PT will be prepared.

Document: Z:\RPL554\AZA40375\Biostatistics\Documentation\SAP\Verona RPL554-DP-201 SAP v2.0 – Part B

Author: [name] / [name]

Version Number: 2.0

Version Date: [08JUL2019]

Template No.: CS TP BS016 Revision 5

Reference: CS WI BS005

Effective Date: 01Apr2018

Copyright © 2009, 2010, 2012, 2016, 2018 IQVIA. All rights reserved. The contents of this document are confidential and proprietary to IQVIA Holdings Inc. and its subsidiaries. Unauthorized use, disclosure or reproduction is strictly prohibited.

16.2. LABORATORY EVALUATIONS

Results from the local laboratory will be included in the reporting of this study for hematology, blood chemistry, and urinalysis. A list of laboratory assessments to be included in the outputs is included in the protocol, Sections 7.4.3.1, 7.4.3.2, and 7.4.3.3 for hematology, blood chemistry, and urinalysis, respectively. Presentations will use International system (SI) units.

Quantitative laboratory measurements reported as “< X”, i.e. below the lower limit of quantification (BLQ), or “> X”, i.e. above the upper limit of quantification (ULQ), will be converted to X for quantitative summaries, but will be presented as recorded, i.e. as “< X” or “> X” in the listings.

The following summaries will be provided for laboratory data:

- Actual and change from baseline (pre-dose at Day 1 for each treatment period) to each pre-dose time point at Day 7 (for quantitative measurements), including overall (where overall is regardless of treatment period, day and timepoint to assess treatment group, as a whole).
- Shift from baseline based on normal range criteria (for quantitative measurements and categorical measurements)
- Incidence of abnormal values according to normal range criteria (in the case of Biochemistry only).
- Listing of all abnormal values occurring after the first dose of study medication.

16.2.1. LABORATORY REFERENCE RANGES AND MARKEDLY ABNORMAL CRITERIA

Quantitative laboratory measurements will be compared with the relevant laboratory reference ranges in SI units and categorized as:

- Low: Below the lower limit of the laboratory reference range.
- Normal: Within the laboratory reference range (upper and lower limit included).
- High: Above the upper limit of the laboratory reference range.

In addition to the high and low quantitative laboratory assignments (as identified by means of the laboratory reference ranges), markedly abnormal quantitative blood chemistry values per the table below will also be identified by the Investigator.

Document: Z:\RPL554\AZA40375\Biostatistics\Documentation\SAP\Verona RPL554-DP-201 SAP v2.0 – Part B

Author: [name] / [name]

Version Number: 2.0

Version Date: [08JUL2019]

Template No.: CS_TP_BS016 Revision 5

Reference: CS_WI_BS005

Effective Date: 01Apr2018

Copyright © 2009, 2010, 2012, 2016, 2018 IQVIA. All rights reserved. The contents of this document are confidential and proprietary to IQVIA Holdings Inc. and its subsidiaries. Unauthorized use, disclosure or reproduction is strictly prohibited.

Blood Chemistry – Markedly Abnormal Definition	
Alanine Aminotransferase (ALT)	> 3 x ULN
Alkaline Phosphatase (ALP)	> 3 x ULN
Aspartate Aminotransferase (AST)	> 3 x ULN
Creatinine	> 221 µmol/L
Gamma Glutamyl Transferase (GGT)	> 3 x ULN
Bilirubin (TBL)	> 3 x ULN

ULN: Upper limit of normal.

16.3. ECG EVALUATIONS

Overall results from the local ECG lab will be included in the reporting of this study. The overall assessment of ECG parameters will be reported for this study:

- Normal
- Abnormal not Clinically Significant (ANCS)
- Abnormal Clinically Significant (ACS)
- Incomplete Analysis
- Uninterpretable

The following summaries will be provided for quantitative ECG data, for example heart rate:

- Actual assessments at baseline (pre-dose at Day 1 for each treatment period) and each pre-dose time point at Day 7, including overall (where overall is regardless of treatment period, day and timepoint to assess treatment group as a whole).
 - Shift of overall assessment baseline to post-dose timepoints per Normal, ANCS and ACS overall assessment criteria.
 - Listing of all ECG evaluations and abnormal values occurring after the first dose of study medication.

Document: Z:\RPL554\AZA40375\Biostatistics\Documentation\SAP\Verona RPL554-DP-201 SAP v2.0 – Part B

Author: [name] / [name]

Version Number: 2.0

Version Date: [08JUL2019]

Template No.: CS_TP_BS016 Revision 5

Reference: CS_WI_BS005

Effective Date: 01Apr2018

Copyright © 2009, 2010, 2012, 2016, 2018 IQVIA. All rights reserved. The contents of this document are confidential and proprietary to IQVIA Holdings Inc. and its subsidiaries. Unauthorized use, disclosure or reproduction is strictly prohibited.

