Study Procedures:	
The following will be performed at each treatment visit:
 
• Measurements of lung function (FEV₁ and forced vital capacity [FVC]) by spirometry
– Screening– Part A: Pre-dose and up to 12 hours post-dose– Part B: Pre-dose up to 12 hours post-dose on Days 1 and 7– End of Study Visit• 12-lead electrocardiogram (ECG)
– Screening– Part A: Pre-dose and up to 8 hours post dose– Part B: Pre-dose on Days 1 and 7• Vital signs
– Screening– Part A: Pre-dose and up to 24 hours post-dose– Part B: Pre-dose and up to 12 hours post-dose on Days 1 and 7– End of Study Visit• PK
– Part A: Pre-dose and up to 24 hours post-dose– Part B: Pre-dose and up to 12 hours post-dose on Days 1 and 7• Laboratory safety tests
– Part A: Screening Part B: Pre-dose on Days 1 and 7 of each treatment period, and at End of Study Visit 
Adverse events will be recorded throughout the study.

Number of Patients Planned:	Approximately 36 randomized patients
Main Criteria for Eligibility:	
Inclusion Criteria
 
Male and female patients with moderate to severe COPD, with a post-bronchodilator FEV₁ of 40 to 80% of predicted and FEV₁/FVC ratio of ≤ 0.70. They must have a baseline increase in FEV₁ of ≥ 150 mL following four puffs of albuterol. They must have at least a 10 pack-year smoking history, and may be either a former smoker or current smoker.
 
Exclusion Criteria
 
Patients must be clinically stable without recent COPD exacerbations or hospitalizations. They must not have uncontrolled disease or chronic heart failure.

Study Treatments:	
Part A (single dose parallel group), administered once in the morning:
 
Treatment Arm 1: RPL554 150 µg double blind Treatment Arm 2: RPL554 500 µg double blind Treatment Arm 3: RPL554 1500 µg double blind Treatment Arm 4: RPL554 3000 µg double blind Treatment Arm 5: RPL554 6000 µg single blind Treatment Arm 6: Placebo single blind
 
Part B (double-blind, repeat dose crossover), administered morning and evening (except morning only on Day 7):
 
Treatment 1: RPL554 150 µg Treatment 2: RPL554 500 µg Treatment 3: RPL554 1500 µg Treatment 4: RPL554 3000 µg Treatment 5: Placebo

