16.4. VITAL SIGNS

The following Vital Signs measurements will be reported for this study:

- Supine Systolic Blood Pressure (mmHg)
- Supine Diastolic Blood Pressure (mmHg)
- Supine Pulse Rate (bpm)

The following summaries will be provided for vital signs data:

- Actual assessments at screening, baseline (pre-dose at each treatment period) and each post-dose time points, including end of study visit and overall (where overall is regardless of treatment period, day and timepoint to assess treatment group as a whole).
- Incidence of markedly abnormal values (number and percent) based on the criteria presented in the table below:

	Low	High
Systolic blood pressure (mmHg)	- ≤ 90 mmHg - Decrease from Baseline of ≥ 40 mmHg	- ≥ 180 mmHg - Increase from Baseline of ≥ 40 mmHg
Diastolic blood pressure (mmHg)	- ≤ 50 mmHg - Decrease from Baseline of ≥ 20 mmHg	- ≥ 110 mmHg - Increase from Baseline of ≥ 20 mmHg
Pulse rate (bpm)	- ≤ 50 bpm - Decrease from Baseline of ≥ 30 bpm	- ≥ 110 bpm - Increase from Baseline of ≥ 30 bpm

Peak supine pulse rate after study medication is defined as the maximum value measured in the first 4 hours post-dose. Peak pulse rate and change from baseline to peak on Day 1 and after morning dosing on Day 7 will be summarized similarly to [Section 15.1.3](#), including the figure presentation described in the same section. Treatment comparisons of change from baseline will be performed using an ANCOVA adjusting for treatment, treatment period and patient, and using pre-dose pulse rate as a covariate, like the hypothesis described in [Section 15.1.3](#). The model will be additive; therefore no log-transformation will be applied.

Document: Z:\RPL554\AZA40375\Biostatistics\Documentation\SAP\Verona RPL554-DP-201 SAP v2.0 – Part B

Author: [name] / [name]

Version Number: 2.0

Version Date: [08JUL2019]

Template No.: CS_TP_BS016 Revision 5

Reference: CS_WI_BS005

Effective Date: 01Apr2018

Copyright © 2009, 2010, 2012, 2016, 2018 IQVIA. All rights reserved. The contents of this document are confidential and proprietary to IQVIA Holdings Inc. and its subsidiaries. Unauthorized use, disclosure or reproduction is strictly prohibited.

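### The Part B *overall* rows for ECG and for actual values of blood laboratory tests pool the untreated Day 1 pre-dose reading with Day 7, so they show about half of any Day 7 pre-dose difference from placebo (minor)

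*SAP*

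**What the plan says.** **ECG (SAP Part B, 16.3).** The quantitative summary is "Actual assessments at baseline (pre-dose at Day 1 for each treatment period) and each pre-dose time point at Day 7", with the pooled row added: "including overall (where overall is regardless of treatment period, day and timepoint to assess treatment group as a whole". The same section adds a shift table of the overall clinical assessment and a listing. It lists no change from baseline for quantitative ECG values. The protocol synopsis gives the ECG schedule as "Part B: Pre-dose on Days 1 and 7", so Part B has no post-dose ECG.

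**Laboratory (SAP Part B, 16.2).** The summary is "Actual and change from baseline (pre-dose at Day 1 for each treatment period) to each pre-dose time point at Day 7 (for quantitative measurements", and it includes "overall (where overall is regardless of treatment period, day and timepoint to assess treatment group, as a whole". Here both actual values and changes are summarised. The protocol synopsis gives the sampling schedule as "Pre-dose on Days 1 and 7 of each treatment period, and at End of Study Visit".

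**Vital signs (SAP Part B, 16.4).** Actual values are summarised at screening, at baseline and at each post-dose time, "including end of study visit and overall (where overall is regardless of treatment period, day and timepoint to assess treatment group as a whole". Peak pulse is handled separately, with its own ANCOVA on change from baseline.

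**Baseline and change.** SAP Part B 6.2 takes the pre-dose reading of each treatment period as the safety baseline. Protocol 9.4.7 asks that, for continuous safety variables, change from that baseline be summarised as well as the values themselves. SAP Part B 3.3 declares no change from the protocol's analyses.

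**The concern.** None of the three definitions of *overall* leaves out the Day 1 pre-dose reading. That reading is taken before the first dose of the period's treatment and, from Treatment Period 2 on, after a washout of 7 to 10 days that the protocol considers adequate. It carries no information about the treatment under whose name it is pooled. The SAP says the row is there to assess the treatment group as a whole; a row made up half of untreated readings does not do that.

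The point matters most for ECG. QTcF and heart rate are named among the Part B secondary safety endpoints (protocol 9.3.2.2), and protocol 1.2 mentions tachycardia in non-clinical work and small transient heart-rate increases at 6 and 12 mg in earlier studies. The Part A SAP (16.3, 16.4) listed change from baseline at each post-dose time for ECG and vital signs and had no *overall* row. The Part B SAP drops the change summary for both and adds the pooled row. A reader who goes to that row for a one-line comparison of doses sees a smaller contrast than the Day 7 data contain.

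**Working it through.** The documents give no figure for this row, so there is nothing to reproduce. The check is a count of readings.

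**Formula.** At readings taken off treatment, the expected active-minus-placebo difference is zero. If the effect is the same at every on-treatment reading, the pooled row shows the fraction

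f = (on-treatment readings) / (all readings pooled).

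**ECG.** There are two readings per period: Day 1 pre-dose (off treatment) and Day 7 pre-dose (on treatment, after the 12 doses of Days 1 to 6). So f = 1/2 = 0.50. For an assumed Day 7 difference d, the row shows (0 + d)/2 = d/2. A simulation with d = 4 units gave 2.0 in the pooled row and 4.0 for change from Day 1 to Day 7.

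**Blood laboratory tests, actual values.** The count per period is the same, so f = 0.50. The SAP does not say whether the End of Study sample enters. If it were counted under the last treatment received, with no residual effect, a patient would contribute 5 × 2 + 1 = 11 readings, 5 of them on treatment: f = 5/11 = 0.45.

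**Missing Day 7 readings (assumed range).** With a fraction m missing, f = (1 − m)/(2 − m):
- m = 0.05: 0.95/1.95 = 0.49
- m = 0.20: 0.80/1.80 = 0.44

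**Blood laboratory tests, change from baseline.** A change exists only at Day 7, so f = 1/1 = 1.00. This row is not diluted unless zero changes at baseline are entered as data.

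**Urinalysis.** Protocol Table 6 shows it on Day 1 and at End of Study but not on Day 7, so the factor of one half does not apply to it.

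**Vital signs.** Protocol 6.4.1 and 6.4.2 give pre-dose and 1, 2, 4, 8 and 12 h on each of Days 1 and 7: 12 readings, 11 on treatment.
- By that text: f = 11/12 = 0.92 (8% dilution)
- By Table 6, which shows no 12 h mark on Day 1: f = 10/11 = 0.91 (9%)
- Text count over five periods plus End of Study: f = 55/61 = 0.90 (10%)
- The same plus screening: f = 55/62 = 0.89 (11%)

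Taking the Table 6 count with both extra visits gives 50/57 = 0.88, just outside that range. All the vital-sign figures assume an equal effect at every on-treatment reading. In practice the row also averages over different times after dosing.

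**The case against.** The strongest reply is that nothing is hidden. Section 16.3 keeps the Day 1 and Day 7 summaries and adds *overall* to them, and protocol 9.4.7 calls for summaries by treatment group and time of collection. The undiluted Day 7 values therefore belong in the same table. Section 16 of the Part B SAP rules out safety comparisons unless a section specifies them. The heart-rate question that is formally analysed, peak pulse on Days 1 and 7, has its own model and does not use this row. Appendix 1 shows *overall* only where applicable, and Section 8 leaves table content to templates that are not part of these documents. All of this stands, and it limits the weight of the point.

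Three stronger readings are tempting, and the documents do not support them.
- A reader might infer that all laboratory results are halved. The change-from-baseline row carries the full Day 7 effect.
- A reader might infer that *overall* is the only by-treatment ECG figure, so that the doses are made to look alike. The Day 7 row remains. Whether it is also split by period depends on the templates.
- A reader might infer that the row counts readings, so that its n is 2 times (ECG, laboratory) or 12 times (vital signs) the number of patients. The SAP gives no aggregation rule for this row, and Section 5.3 points the other way: in by-treatment analyses a patient counts once for each time that treatment was received.

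What survives is that the stated definition, applied as written, does not serve its stated purpose.

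**Conclusion.** The point holds, as a minor fault in descriptive safety output. In Section 16.3, and for actual values of blood tests in Section 16.2, the *overall* row shows about half of any Day 7 pre-dose difference from placebo: 0.50 with complete pairs, and 0.44 to 0.49 under the missing-data and End of Study assumptions above. Only the Day 7 pre-dose difference is in question, since Part B takes no post-dose ECG or blood sample for safety. For vital signs the loss is about 8 to 11% and would change little by itself.

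The result rests on two things: the literal wording, which excludes no day or time point, and the absence of any treatment effect at Day 1 pre-dose, which follows from the washout. No test, efficacy endpoint or analysis set depends on the row. The absence of a change-from-baseline summary for quantitative ECG and vital signs, although protocol 9.4.7 asks for one, is why the row is worth correcting.

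**What to change.** In SAP Part B 16.2, 16.3 and 16.4:

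1. Define *overall* as readings taken after the first dose of that period's treatment. Exclude Day 1 pre-dose, screening and End of Study, which can keep rows of their own. That leaves Day 7 pre-dose for ECG and blood tests, and for vital signs the Day 1 post-dose readings with all Day 7 readings.
2. State that each patient contributes one value per treatment, the mean of that patient's eligible readings.
3. Add change from that period's Day 1 pre-dose value for quantitative ECG and for vital signs, to bring the SAP into line with protocol 9.4.7.

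For ECG and blood-test actual values, the redefined row equals the Day 7 row pooled over periods. If the templates already show that row, *overall* can be dropped there. The cost is SAP wording, a filter in the programs and the added change tables. No new data are needed, and no test is affected.

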16.4. VITAL SIGNS

The following Vital Signs measurements will be reported for this study:

- Supine Systolic Blood Pressure (mmHg)
- Supine Diastolic Blood Pressure (mmHg)
- Supine Pulse Rate (bpm)

The following summaries will be provided for vital signs data:

- Actual assessments at screening, baseline (pre-dose at each treatment period) and each post-dose time points, including end of study visit and overall (where overall is regardless of treatment period, day and timepoint to assess treatment group as a whole).
- Incidence of markedly abnormal values (number and percent) based on the criteria presented in the table below:

	Low	High
Systolic blood pressure (mmHg)	- ≤ 90 mmHg - Decrease from Baseline of ≥ 40 mmHg	- ≥ 180 mmHg - Increase from Baseline of ≥ 40 mmHg
Diastolic blood pressure (mmHg)	- ≤ 50 mmHg - Decrease from Baseline of ≥ 20 mmHg	- ≥ 110 mmHg - Increase from Baseline of ≥ 20 mmHg
Pulse rate (bpm)	- ≤ 50 bpm - Decrease from Baseline of ≥ 30 bpm	- ≥ 110 bpm - Increase from Baseline of ≥ 30 bpm

Peak supine pulse rate after study medication is defined as the maximum value measured in the first 4 hours post-dose. Peak pulse rate and change from baseline to peak on Day 1 and after morning dosing on Day 7 will be summarized similarly to [Section 15.1.3](#), including the figure presentation described in the same section. Treatment comparisons of change from baseline will be performed using an ANCOVA adjusting for treatment, treatment period and patient, and using pre-dose pulse rate as a covariate, like the hypothesis described in [Section 15.1.3](#). The model will be additive; therefore no log-transformation will be applied.

Document: Z:\RPL554\AZA40375\Biostatistics\Documentation\SAP\Verona RPL554-DP-201 SAP v2.0 – Part B

Author: [name] / [name]

Version Number: 2.0

Version Date: [08JUL2019]

Template No.: CS_TP_BS016 Revision 5

Reference: CS_WI_BS005

Effective Date: 01Apr2018

Copyright © 2009, 2010, 2012, 2016, 2018 IQVIA. All rights reserved. The contents of this document are confidential and proprietary to IQVIA Holdings Inc. and its subsidiaries. Unauthorized use, disclosure or reproduction is strictly prohibited.

16.5. PHYSICAL EXAMINATION

The following summaries will be provided for the full physical examination data, covering major body systems (nose, throat, skin, thyroid gland, neurological system, respiratory system, cardiovascular system, abdomen [liver and spleen], lymph nodes and extremities):

- Incidence of abnormalities at end of study visit (4-10 days after last treatment period).
- Shifts from baseline at end of study visit.

The following summaries will be provided for a brief physical examination to be also performed, on skin, respiratory system, cardiovascular system, and abdomen (liver and spleen):

- Incidence of abnormalities pre-dose on Day 1 and 7 by treatment period.
- Shifts from baseline by treatment period and timepoint.

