5.6 Method of Assigning Patients to Treatment Groups

All patients consented will be assigned a patient identification number upon signing of the informed consent using the following convention: XXX-YYY where XXX is the center number and YYY is the patient number (001, 002, etc.).

In Part A of the study, patients will be randomly assigned to receive a single dose of one of six possible treatments (see Section 5.1.1). In Part B, patients will again be randomized and assigned to a set of selected treatment sequences balanced with respect to both period and first-order carry-over effects (see Section 5.1.2). Available randomization numbers must be used sequentially for the next enrolled patient, to determine the treatment dose to be dispensed and administered.

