7.4.5 Physical Examination

A full physical examination, covering major body systems (assessments of the nose, throat, skin, thyroid gland, neurological system, respiratory system, cardiovascular system, abdomen [liver and spleen], lymph nodes and extremities) will be performed at Screening. Results will be recorded in the eCRF as normal, abnormal not clinically significant or abnormal clinically significant and abnormal results described. The full physical examination will be repeated at the End of Study Visit, and any changes only recorded.

A brief physical examination, including assessments of the skin, respiratory system, cardiovascular system, and abdomen (liver and spleen) will be performed pre-dose for Part A, and pre-dose on Days 1 and 7 for Part B.

7.4.6 12-Lead ECG

Each 12-lead ECG should be taken after at least 5 minutes in the supine position. An overall assessment (normal, abnormal not clinically significant or abnormal clinically significant) will be recorded in the eCRF by the Investigator. ECG recordings will be assessed locally.

Post-dose measurements in Part A will be taken in relation to the single, morning dose of RPL554 or placebo.

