9.4.7 Safety

Safety data including laboratory safety tests, 12-lead ECG, vital signs and physical examinations, will be summarized by treatment group and timepoint of collection, when appropriate, for each of the two parts separately. For continuous variables, the change from baseline (pre-dose at each treatment period) to each post-dose time point will also be calculated and summarized. Data will further be illustrated by shift tables (showing changes from low/normal/high) and shift plots for selected time points. Separate listings will be generated of abnormal values occurring after the first dose of study treatment.

In Part A, change from baseline in peak pulse and peak heart rate will be compared between the treatments using analysis of covariance models with fixed factor treatment, and using the pre-dose baseline value as a covariate. In Part B, change from baseline in peak pulse will be compared between the treatments using analysis of covariance models with fixed factors for treatment, period and patient, and using the pre-dose Day 1 baseline value as a covariate. Additive model will be used for pulse and heart rate.

Coded adverse event terms will be presented by system organ class (SOC) and preferred term and summarized by treatment group for each part. Summary tables by treatment group with total number and number of patients with adverse events, SAEs, adverse events leading to discontinuation of study treatment, causally related adverse events and severe adverse events will be produced. Further SAEs, causally related adverse events and adverse events of each intensity will be summarized by SOC and preferred term.

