3.3. CHANGES TO ANALYSIS FROM PROTOCOL

None.

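### SAP Part B 16.5 tabulates the brief physical examination by treatment period and names no treatment group, so the summary as written does not compare doses with placebo (minor)

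*SAP*

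**What the plan says.** Protocol 9.4.7 lists physical examinations among the safety data: "physical examinations, will be summarized by treatment group and timepoint of collection, when appropriate, for each of the two parts separately". Protocol 7.4.5 schedules the brief examination "pre-dose on Days 1 and 7 for Part B".

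SAP Part B 16.5 gives two summaries for that examination: "Incidence of abnormalities pre-dose on Day 1 and 7 by treatment period" and "Shifts from baseline by treatment period and timepoint". Treatment group is not mentioned anywhere in 16.5. Section 3.3 of the same SAP, headed "CHANGES TO ANALYSIS FROM PROTOCOL", reads None.

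The neighbouring safety sections differ. For laboratory values, 16.2 adds an overall presentation, "where overall is regardless of treatment period, day and timepoint to assess treatment group, as a whole", and 16.3 and 16.4 carry near-identical wording for ECG and vital signs. Section 16.5 has no such line.

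The trial is a five-period, five-treatment crossover. Protocol 5.6 describes the sequences as "balanced with respect to both period and first-order carry-over effects", and SAP Part B Appendix 1 lists ten of them.

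**The concern.** In a crossover, period and treatment are different factors, and the design deliberately makes them orthogonal. A safety table indexed by period shows whether findings drift over calendar time or successive visits. It does not show whether they go with the drug.

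Safety and tolerability of repeat doses is a secondary objective of Part B (protocol 2.2.2). The Day 1 pre-dose examination is the baseline of each period, so the Day 7 pre-dose examination, which follows 12 doses (Days 1 to 6, twice daily), is the only one on treatment within a period. A reader would want that examination set against placebo, dose by dose. Followed literally, 16.5 does not supply this, and 3.3 does not say that the grouping differs from the protocol's.

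**Working it through.** **1. Is the design balanced as stated?** The table gives the sequence numbers from SAP Part B Appendix 1 that contain each treatment in each period.

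| Period | 150 µg | 500 µg | 1500 µg | 3000 µg | Placebo |
|---|---|---|---|---|---|
| 1 | 1, 2 | 3, 4 | 5, 6 | 7, 8 | 9, 10 |
| 2 | 4, 9 | 5, 10 | 1, 7 | 2, 3 | 6, 8 |
| 3 | 3, 6 | 7, 9 | 4, 8 | 1, 10 | 2, 5 |
| 4 | 7, 8 | 1, 2 | 9, 10 | 5, 6 | 3, 4 |
| 5 | 5, 10 | 6, 8 | 2, 3 | 4, 9 | 1, 7 |

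Every cell holds exactly two sequences. All 20 ordered pairs of successive treatments also occur, each exactly twice. The balance for period and first-order carry-over claimed in protocol 5.6 is reproduced.

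**2. What does a table by period alone contain?** With equal numbers per sequence and no dropout, each period has 2/10 = 1/5 of patients on each treatment. Let *r* be the Day 7 abnormality rate on 3000 µg and *b* the rate on each of the other four treatments. The expected rate in every period is

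(*r* + 4*b*)/5.

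This does not depend on the period, so whatever *r* and *b* are, the expected difference between periods is zero.

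**3. Illustration.** The documents give no rates, so these are assumptions. The 30 completers come from protocol 9.5 and 4.3.4.

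- *r* = 20%, *b* = 0. By treatment: 30 × 0.20 = 6/30 on 3000 µg against 0/30 on placebo. By period: 0.20/5 = 4%, an expected 1.2/30 in each of the five periods.
- *r* = 20%, *b* = 2%. By treatment: 20% against 2%. By period: (0.20 + 4 × 0.02)/5 = 5.6% in each period.

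**4. What if period is nested within treatment?** Each treatment-by-period cell then holds 30/5 = 6 patients. Adding the five period rows under a treatment gives 5 × 6 = 30, so the 6/30 against 0/30 can be recovered by hand. Nothing is diluted, but the pooled treatment row is not specified.

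**The case against.** The strongest reply is that little is lost.

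- **Individual findings stay traceable.** Appendix 1 of the Part B SAP requires all CRF variables with data to be listed and orders safety listings by treatment received. Protocol 9.4.7 also promises listings of abnormal values after first dose. A reader might infer from 16.5 that no abnormality could be related to a dose or to placebo. The documents do not support that.
- **Clinically important findings have another route.** The protocol's adverse event definition covers worsening, and events observed by site staff are recorded. SAP 16.1 assigns treatment-emergent events to the treatment actually received.
- **The protocol statement is qualified.** Protocol 9.4.7 asks for the treatment-group summary only where appropriate, so 16.5 is not a breach of an absolute requirement.
- **Silence is weak evidence.** The overall wording in 16.2 to 16.4 is attached to the bullets on actual values. The categorical bullets there (laboratory shifts and incidence, ECG shifts, vital-sign incidence) also leave treatment group implicit. Section 8 refers to templates that are not among the documents, and Appendix 1 speaks of tables with treatments as columns. Period may therefore be a row breakdown within treatment columns.

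All four points stand as limits on the concern. They do not remove it. A listing gives no incidence or shift by dose. The qualifier does not explain putting period in place of treatment at the one on-treatment examination. Where the layout is open, the SAP text should settle it, and the only grouping factor it names for these tables is not the protocol's.

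**Conclusion.** The point holds as a minor reporting defect. SAP Part B 16.5 names a different grouping factor from protocol 9.4.7, and 3.3 does not declare the difference. Read literally, the two brief-examination tables carry no contrast between doses and placebo. Read as period within treatment, they give cells of about 6 patients and lack a pooled treatment row.

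The exact cancellation in a period-only table assumes equal allocation to the ten sequences and no dropout. With the planned 36 patients (36/10 = 3.6 per sequence), or after withdrawals, the mix is only approximately equal. The 6/30 and 1.2/30 figures rest on assumed rates and on the period-only reading.

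Physical examination is not itemised among the Part B safety endpoints in protocol 9.3.2.2. No endpoint test, sample size, power or error rate is touched. A reader might go further and conclude that a dose-related harm would be hidden from the study report. The listings and the adverse event tables by actual treatment do not support that.

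**What to change.** In SAP Part B 16.5, specify for the brief examination:

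- incidence of abnormalities at Day 1 pre-dose and Day 7 pre-dose, by actual treatment received and day, pooled over periods;
- shift from Day 1 pre-dose to Day 7 pre-dose of the same period, by actual treatment received, pooled over periods;
- treatment period as an optional breakdown or as a column in the listing.

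This fits the rule already in section 5.3, which counts a patient once for each time a treatment was received. If a period layout is wanted for a reason, declare and justify it in 3.3 instead. The cost is a few words of SAP text and the matching table shell, with no new data.
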